 - (1) “The purpose of this test is to find your judgments of the loudness of different sounds. You will hear sounds that increase and decrease in volume. You must make a judgment about how loud the sounds are. Pretend you are listening to the radio at that volume. How loud would it be? After each sound, tell me which of these categories best describes the loudness. Keep in mind that an uncomfortably loud sound is louder than you would ever choose on your radio no matter what mood you are in.”
- c. Stimuli: warble tone at 500 Hz followed by 3000 Hz
- d. Participant will respond to varied presentation levels on seven-point scale of loudness using the Categories of Loudness (1-8) as a reference.
- e. Procedure: start at threshold and use an ascending approach in 5 dB steps until an “uncomfortably loud” response is obtained. Return to threshold and repeat for a total of 4 times.
- f. The median of the values obtained on four runs may be assumed to represent the loudness percept in each category.

- g. Record on audiogram.
7. Put bone vibrator on participant's mastoid and administer pure-tone bone-conduction (BC) testing using ASHA standard procedures using the GSI 61 audiometer. Set "transducer" to "bone".
- a. BC test frequencies: 250, 500, 1000, 1500, 2000, 3000, and 4000 Hz. Apply masking as needed.
8. To be eligible for ABCD, participant's hearing thresholds need to be bilaterally symmetrical and within a mild to moderate sensorineural hearing loss range, and within fitting range of hearing aid. *See shaded region on Audiogram (1-6).
- a. Asymmetry: more than 20 dB difference at any one frequency 250-2000 Hz makes participant ineligible.
 - b. Participant may have one threshold at a single frequency in each ear that is outside the shaded area by ≤ 10 dB and still be eligible for study.
 - c. If participant's thresholds are close to, but outside our accepted range, "flag" the file and notify PI and CTC.
 - d. If participant is eligible, continue with unaided CST.
 - e. If ineligible, counsel (see H below).
- (1) Note on audiogram if a referral to ENT was made or other advice was given.

G. UNAIDED CST (CONNECTED SPEECH TEST) FORM (1-9)

- 1. Audiometer settings:
 - a. Track 1: Calibrate—complete prior to every test
 - b. Channel 1: 50 dB HL, External A, Left (front speaker), Speaker
 - c. Channel 2: 46 dB HL, External B, Right (back speaker), Speaker

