2. Instructions: “You will hear a woman talking from in front of you. There will be noise behind you. Ignore the background noise, and try to repeat back what the woman says. She will say one sentence at a time. Each group of sentences has a topic. The first topic is “window.” Do you have any questions?”
3. Present CST (track 32) at 50 dB HL from loudspeaker located at 0° azimuth and elevation with the multi-talker babble from the CST presented at 46 dB HL (+3 dB signal-to-babble ratio) from an identical loudspeaker located at 180° azimuth and 0° elevation.
4. Have participant complete two passage pairs (“window” and “glove”; 50 total key words). Give participant second passage topic prior to starting second passage.
5. Present sentences one at a time, pausing the CD after each sentence to score.
6. Key words are capitalized and bolded on Unaided CST Form (1-9). To score, cross out key words that are repeated incorrectly or are not repeated at all.
7. Participant must repeat the word exactly as written for correct response. Any other variation of the word, incorrect word, or absence of the word should be marked incorrect.
8. Score = total number of correct words. Record as percentage score next to total correct score.

H. COUNSELING

1. Ask participant if anyone is waiting in the waiting room that he or she would like to have present during counseling re: hearing test. If yes, go get person in waiting room.
2. Counsel participant regarding audiologic evaluation results.
3. If participant is ineligible, escort out of building and inform CTC that participant’s

tentative appointment needs to be cancelled. Exit Form # 1 (1-10) is completed and signed at this time. If participant's thresholds were close to our acceptable range, notify participant that we will contact him or her if requirements change.

I. MMSE-2 SV (MINI MENTAL STATE EXAMINATION, SECOND EDITION, STANDARD VERSION) (1-11)

1. Follow the instructions on the MMSE-2 SV (1-11). Participant needs to score at least 26/30 to pass. Record the score on the MMSE-2 SV (1-11).
2. If participant is still eligible, continue to Case History.

J. CASE HISTORY (1-12)

1. Ask the participant to fill out this form with a black pen. Be available for any questions that may arise while filling it out. If the participant has a lengthy list of medications, make a copy of this and staple it to the case history form.

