 - (1) Track 1: Calibrate—complete prior to every test
 - (2) Channel 1: 50 dB HL, External A, Left (front speaker), Speaker
 - (3) Channel 2: 46 dB HL, External B, Right (back speaker), Speaker
 - e. Instructions: “You will hear a woman talking from in front of you. There will be noise behind you. Ignore the background noise, and try to repeat back what the woman says. She will say one sentence at a time. Each group of sentences has a topic. The first topic is “umbrella”. Do you have any questions?”
 - f. Present CST (track 33) at 50 dB HL from loudspeaker located at 0° azimuth and elevation with the multi-talker babble from the CST presented at 46 dB HL (+3 dB signal-to-babble ratio) from an identical loudspeaker located at 180° azimuth and 0° elevation.
 - g. Have participant complete two passage pairs (“umbrella” and “giraffe”; 50 total key words). Provide participant with second passage topic prior to starting second passage.
 - h. Present sentences one at a time, pausing the CD after each sentence to score.
 - i. Key words are capitalized and bolded on the scoring sheet. To score, cross out key words that are repeated incorrectly or are not repeated at all.
 - j. Participant must repeat the word exactly as it is to get it correct. Any other variation of the word, incorrect word, or absence of the word should be marked incorrect.
 - k. Score = total number of correct words
3. Draw shade to cover window so that A4, who will sit on tester side while participant does surveys on tablet, can’t see what A1/A2 are doing during hearing aid inspection.

4. Seat participant at tympanometry table and remove hearing aids to complete otoscopy and record on Hearing Aid Inspection Checklist (3-2).
 - a. Bring otoscope to participant side of audio booth to assist with hearing aid inspection.
5. Page A4 using one button pager to notify A4 that participant is ready to complete surveys on tablet (see F below) while A1/A2 complete steps C-E.

C. PHYSICAL INSPECTION OF HEARING AIDS (3-2)

1. A1/A2 completes Hearing Aid Inspection Checklist (3-2).
 - a. Do not open battery door until after electroacoustic exam is complete.
2. Otoscopy (status of EAC and pinna should be recorded on checklist)
3. Physical examination of as-worn hearing aids
 - a. Visual inspection of ear tips or tubing to check for breaks or cerumen occlusion
 - b. Record on the checklist.

D. AS-WORN SIMULATED SPEECHMAP (RIGHT, THEN LEFT) (3-2)

1. Couple hearing aid to ITE coupler using new sticky tack.

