1. A4 will have participant follow instructions and complete the surveys on the tablet. Participant will page A4 with one-button pager when finished with each survey and A4 will start the next survey until all three surveys are complete.

G. POST-MAINTENANCE AIDED CST FORM (3-3)

1. A4 instructs participant to sit in designated chair (make sure chair is located in correct position on floor).
2. A4 places participant’s hearing aids in ears.
3. Audiometer settings:
 - a. Track 1: Calibrate (already completed by A1/A2)
 - b. Channel 1: 50 dB HL, External A, Left (front speaker), Speaker
 - c. Channel 2: 46 dB HL, External B, Right (back speaker), speaker
4. Instructions: “You will hear a woman talking from in front of you. There will be noise behind you. Ignore the background noise, and try to repeat back what the woman says.

She will say one sentence at a time. Each group of sentences has a topic. The first topic is “nail”. Do you have any questions?”

5. Present CST (track 33) at 50 dB HL from loudspeaker located at 0° azimuth and elevation with the multi-talker babble from the CST presented at 46 dB HL (+3 dB signal-to-babble ratio) from an identical loudspeaker located at 180° azimuth and 0° elevation.
6. Have participant complete two passage pairs (“nail” and “woodpecker”; 50 total key words). Provide participant with second passage topic prior to starting second passage.
7. Present sentences one at a time, pausing the CD after each sentence to score.
8. Key words are capitalized and bolded on the scoring sheet. To score, cross out key words that are repeated incorrectly or are not repeated at all.
9. Participant must repeat the word exactly as it is to get it correct. Any other variation of the word, incorrect word, or absence of the word should be marked incorrect.
10. Score = total number of correct words

H. PHAST-R (PRACTICAL HEARING AID SKILLS TEST-REVISED) (T-6)

1. A4 escorts the participant to the tester side of the booth.
2. Instructions: Place the following items in front of the participant: A telephone, different size batteries (10, 312, 13, 675), magnetic tool for battery removal, cleaning tools: brush, cloth, wax loop, plastic “wire” tube cleaner.
3. Use PHAST-R (T-6) score sheet on tablet to rate participant’s performance on each item.

I. MUSIC/TRAINING QUESTIONNAIRE (3-4)

1. Administer Music/Training Questionnaire (3-4).

J. FINAL HEARING AID DECISION FORM #1 (3-5)

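### Do the CST settings contradict the stated +3 dB ratio, and does the repeated track 33 put the Session 3 scores in doubt?

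*Protocol*

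**What the plan says.** The Protocol gives the CST five times: unaided (I. Session 1, G), as-worn and post-maintenance in III. Session 3 (B and G), and as-worn and post-maintenance in IV. Session 3B (B and G). The audiometer lines are the same each time: "Channel 1: 50 dB HL, External A, Left (front speaker), Speaker" for speech and "Channel 2: 46 dB HL, External B, Right (back speaker), Speaker" for babble. The presentation step then repeats both levels and labels the result, with babble "presented at 46 dB HL (+3 dB signal-to-babble ratio").

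On calibration, the first CST of each session carries the line "Track 1: Calibrate—complete prior to every test". The second CST in Session 3 has "Track 1: Calibrate (already completed by A1/A2"), and Session 3B has an equivalent line. None of these lines states an offset between the channels.

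On material, Session 1 has "Present CST (track 32) at 50 dB HL from loudspeaker" for the window and glove passages. Session 3, B.2.f has "Present CST (track 33) at 50 dB HL from loudspeaker", followed in B.2.g by "two passage pairs (“umbrella” and “giraffe”; 50 total key words"). Session 3, G.5 cites track 33 again, this time for nail and woodpecker. Session 3B uses tracks 40 and 51.

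**The concern.** The CST is a measured outcome, and its unaided score places each participant in a low, medium or high stratum for randomisation (I. Session 1, N.5.a). These lines are the operating instructions for it. A difference of 4 dB labelled as 3 dB, repeated five times, reads as an arithmetic error in a test condition. If so, the reported difficulty of the test would be misdescribed, and anyone replicating it could not tell whether to set 3 or 4 dB.

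The track number looks more serious. If track 33 holds only one of the two Session 3 passage sets, following the text literally would play one set while the other is scored. That score would not measure speech recognition at all, in a session where both CSTs are taken before group assignment is revealed and any reprogramming is done.

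**Working it through.** **Ratio.** Inputs: the speech level, babble level and label in each of the five instructions.

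| CST | Speech (dB HL) | Babble (dB HL) | Difference (dB) | Label (dB) | Offset needed (dB) |
|---|---|---|---|---|---|
| Session 1, unaided | 50 | 46 | 4 | 3 | −1 |
| Session 3, as-worn | 50 | 46 | 4 | 3 | −1 |
| Session 3, post-maintenance | 50 | 46 | 4 | 3 | −1 |
| Session 3B, as-worn | 50 | 46 | 4 | 3 | −1 |
| Session 3B, post-maintenance | 50 | 46 | 4 | 3 | −1 |

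Difference = speech − babble. Offset needed = label − difference = 3 − 4 = −1 dB. The stated +3 dB therefore does not follow from the settings alone. With no offset it would need babble at 50 − 3 = 47 dB HL or speech at 46 + 3 = 49 dB HL.

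The subtraction equals the delivered ratio only if both channels produce the same output for the same dial reading. Speech and babble enter by different inputs (External A and External B) and leave by different loudspeakers. A fixed −1 dB between channels would make all five labels right. Of the five calibration lines, three say to run the calibration track and two say it has been done. None gives a value, so the document supports neither reading over the other.

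**Consequence of the ratio.** Let *c* be the acoustic condition actually delivered, and Y(*c*) a participant's score under it.

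- Between arms, the contrast is mean Y(*c*) in one arm minus mean Y(*c*) in another. The same *c* is specified for all arms, and the label does not enter.
- Aided against unaided: Sessions 1, 3 and 3B specify the same *c*, so the change score does not mix two conditions.
- Strata: the limits (at most 40%, between 40% and 68%, at least 68%) apply to the observed percentage. Calling *c* 3 dB or 4 dB leaves that percentage, and the stratum, where it was.

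**Tracks.** Inputs: the track and topics cited in each instruction.

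| CST | Track | Topics used |
|---|---|---|
| Session 1, unaided | 32 | window, glove |
| Session 3, as-worn (B.2.f) | 33 | umbrella, giraffe |
| Session 3, post-maintenance (G.5) | 33 | nail, woodpecker |
| Session 3B, as-worn | 40 | donkey, guitar |
| Session 3B, post-maintenance | 51 | ear, liver |

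Five passage sets cite four track numbers. Three readings fit:

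1. Track 33 holds all four topics, and both citations are right. The table counts only topics the Protocol uses, and the Protocol does not say how many a track contains.
2. G.5 has the wrong number.
3. B.2.f has the wrong number.

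Nothing in the text separates readings 2 and 3, so neither Session 3 CST can be singled out as exposed or cleared.

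**Consequence of the track number.** Under reading 2 or 3, literal use would pair one set of sentences with another set's scoring sheet. In both instructions the audiologist announces the first topic, stops the CD after each sentence and marks printed key words (Session 3, B.2.e to B.2.i and G.4 to G.8). A wrong set would fail to match the topic and the sheet at the first sentence, and the tester could then find the right track.

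**The case for a change.** The best case for acting is that the manual exists to standardise delivery, and here it disagrees with itself on an operating figure. The levels appear both in the audiometer settings and in the presentation step, so this is not a stray misprint. The two loudspeakers are described as identical, so the text offers no loudspeaker difference to explain the missing 1 dB. The track numbers follow no regular step, so the intended number cannot be inferred without the disc. The Protocol also carries a note, in I. Session 1, N.5.b, that it was edited after completion to record what took place, so correcting the record would fit its purpose, at the cost of a few words and a look at the disc.

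Much of this stands: the mismatch and the duplication are real, and a replicator would want both settled. It does not show that a wrong ratio was delivered or a wrong track played. Identical loudspeakers do not rule out a difference between the two inputs. The obvious edit, relabelling the ratio +4 dB, could replace a correct calibrated value with a wrong one. Correcting the track in G.5 alone would assume where the slip lies. Any edit made now would also leave the tests as they were run.

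**Conclusion.** No change to the plan follows. The ratio point is a nominal 1 dB mismatch between settings and label in five of five instructions, with no effect on any contrast between arms, any aided-unaided change or any stratum. The track point is one number used for two of five passage sets. It is probably clerical, with no evidence of mis-scored tests and with safeguards in the procedure that would expose a wrong track at once.

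This rests on two assumptions: that the stated levels were used in all arms and sessions, as the text directs, and that testers scored against the printed sheets. If a Session 3 scoring form recorded that the wrong track was played, that score would need separate handling, but nothing in the Protocol suggests one does. A low score alone would not be such evidence. Whoever reports the test condition can give the settings and the label together and consult the calibration and the disc if they are available. That is ordinary care in reporting and does not alter the design or the analysis.
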